
Treatment Summary:
	
KTD (maximum of 6 x 28 day cycles) KTD protocol
 
Days 1, 8,15 30 minute IV infusions of Carfilzomib at current dose level.
 
All patients will receive Carfilzomib at 20mg/m² on day 1 of cycle 1 and then registered dose level on day 8 of cycle 1 onwards. The dose levels are:
 
 • level -1- 27mg/m² • level 0 – 36mg/m² • level 1 – 45mg/m²

	
 level 2 - 56mg/m^{2s} 
Days 1-28 50mg Thalidomide, oral preparation for cycle 1 Up to 100mg can be considered for cycle 2 onwards
 
Days 1, 8,15 20mg Dexamethasone, oral preparation
 
A maximum of 6 cycles will be administered.

Anticipated duration of recruitment:	24 months
Duration of patient follow up:	Minimum 6 months after registration or 1 month after last cycle for each patient.
Definition of end of trial:	The end of trial is defined as the date of the last participant's last data item. At this point, the end of trial notification will be submitted to the relevant regulatory authorities (e.g. UK MHRA) and ethics committees.

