13.2 Reporting Procedures

13.2.1 All Adverse Events (AEs)

All adverse events that occur between informed consent and 30 days post last trial treatment administration must be recorded in the patient notes and the trial CRFs. Those meeting the definition of a Serious Adverse Event (SAE) must also be reported to LEEDS CTRU within 24 hours of becoming aware of the event using the trial specific SAE Report. Also refer to section 13.2.2 (Serious Adverse Events (SAEs)).

Pre-existing conditions do not qualify as adverse events unless they worsen.

Overdoses

All accidental or intentional overdoses, whether or not they result in adverse events, must be recorded in the patient notes and CRFs. Overdoses resulting in an adverse event are classified as SAEs and must be reported to LEEDS CTRU according to SAE reporting procedures. The fact that an overdose has occurred must be clearly stated on the SAE Report. Also refer to section 13.2.2 (Serious Adverse Events (SAEs)).

Sites must inform LEEDS CTRU immediately when an overdose has been identified. Also refer to section 17 (Incident Reporting and Serious Breaches).

Adverse Event Term

An adverse event term needs to be provided for each adverse event, preferably using the term listed in the Common Terminology Criteria for Adverse Events (CTCAE) version 4.03, available online at: http://evs.nci.nih.gov/ftp1/CTCAE/CTCAE_4.03_2010-06-14_QuickReference_8.5x11.pdf

Severity

Severity for each adverse event will be determined by using the Common Terminology Criteria for Adverse Events (CTCAE) version 4.03 as a guideline, wherever possible. The criteria are available online at: http://evs.nci.nih.gov/ftp1/CTCAE/CTCAE_4.03_2010-06-14_QuickReference_8.5x11.pdf. Appendix 5 also details some toxicity criteria.

In those cases where the CTCAE criteria do not apply, severity should be coded according to the following criteria:

- 1 = Mild (awareness of sign or symptom, but easily tolerated)
- 2 = Moderate (discomfort enough to cause interference with normal daily activities)
- 3 = Severe (inability to perform normal daily activities)
- 4 = Life threatening (immediate risk of death from the reaction as it occurred)
- 5 = Fatal (the event resulted in death)

Causality

The PI, or other delegated site investigator, must perform an evaluation of causality for each adverse event. Causal relationship to each trial treatment must be determined as follows:

- **None**
There is no evidence of any causal relationship.
- **Unlikely**

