18.0 Endpoints

18.1 Primary endpoints

Dose-Limiting Toxicities (Dose escalation phase), between the time of receiving the first registered dose of Carfilzomib in cycle 1 and day 1 cycle 2, in order to establish the Maximum Tolerated Dose (MTD) and recommended dose (RD) of Carfilzomib in combination with Thalidomide and Dexamethasone.

Proportion of patients treated who experience any grade 3 or 4 CTCAE toxicity throughout all treatment cycles

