2.3 Derivation of endpoints

2.3.1 Primary endpoints

Dose limiting toxicities (DLTs) will be collected from the time of receiving the first dose of Carfilzomib in cycle 1 up to the first dose of treatment administered in cycle 2. Only DLTs that are attributed to the registered dose of Carfilzomib will be included when determining the MTD. A DLT will be defined as any of the following events that are determined to be related to trial drug administration:

1. Any non-haematological toxicity \geq Grade 3 according to NCI CTCAE Version 4.03 which fails to return to \leq Grade 1 or baseline after 7 days. Nausea, vomiting, diarrhoea and electrolyte imbalances will be considered DLTs only if they reach \geq Grade 3 severity despite adequate supportive care measures. Similarly, fluid retention or worsening symptoms of heart failure will be considered as DLTs if they are persistent \geq Grade 3 despite increase in oral diuretics or there is an increase in dyspnoea by \geq 2 NYHA grades within 12 hours of administration of Carfilzomib which persists for $>$ 6 hours or needs hospital admission
2. Grade 4 neutropenia lasting $>$ 7 days or Grade 4 neutropenia with sepsis despite adequate supportive measures.
3. Any grade 4 thrombocytopenia which fails to return to Grade 2 within 7 days without platelet support
4. Delay of $>$ 8 days within cycle 1 or delay of commencement of 2nd cycle by more than 14 days, due to significant toxicity or tolerability issue*
5. Any other event which, in the opinion of the Safety Review Committee, is considered to be clinically significant and related to treatment

The MTD is defined as the highest dose level at which no more than 1 patient experiences a DLT, from the time of receiving the first registered dose of Carfilzomib in cycle 1 up to the first dose of treatment administered in cycle 2, i.e. the dose level below that at which 2 or more patients experiences a DLT. If no more than one patient experiences a DLT at the highest dose level then this will be considered as the MTD.

Once the MTD has been established, a minimum of 6 patients will be treated at this dose level in order to establish the RD. The RD is the dose which will be used in the dose expansion phase of the study to evaluate activity.

The proportion of patients treated who experience any grade 3 or 4 CTCAE toxicity will be calculated as number of patients who experience any grade 3 or 4 CTCAE toxicity throughout their treatment cycle.

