5.1 General calculations

Unless otherwise stated, percentages will be calculated using the total number of patients in the appropriate population as the denominator (i.e. including all patients with missing data for that variable). All analyses will be carried out using SAS unless stated otherwise.

All percentages and means will be rounded to 1 decimal place and standard deviations to 2 decimal places. Values that are below the limit of detection and therefore non-quantifiable will be summarised using the limit of quantification value. For listings, if required, the non-quantifiable value would be reported as an inequality.

Summaries are divided into those participants treated at the recommended dose either during the dose escalation phase (prior to the identification of the recommended dose) or during the dose expansion phase (RD population), and all other participants treated during the dose escalation phase at dose levels other than the recommended dose (Non-RD population). The non-RD population will be split by dose level.

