5.3.2 Primary endpoints

The number of patients experiencing DLTs within the first cycle of KTD will be presented, with descriptive summaries of the specific DLTs observed. Summaries will be presented for each dose level. This data will be presented for patients registered to the dose escalation phase of the study only.

Further summaries of longer-term tolerability will also be presented for patients registered to the dose escalation phase to include the maximum toxicity grade experienced within the first three cycles of treatment, overall and by cycle. Individual listings of the toxicities, grade and cycle of all toxicities experienced within the first three cycles will be presented.

The number of patients experiencing any grade 3 or 4 CTCAE toxicity within all cycles of treatment will be summarised. This will be presented overall and by dose cohort, across all cycles as well as by each cycle.

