5.3.2 Secondary endpoints

Safety and toxicity profiles for each cycle and cohort: data will be summarised descriptively, including the proportion of patients experiencing at least one SAE, the number of SAEs experienced per participant, and the number of SAEs experienced according to seriousness criteria, causality, and body system. Toxicity will be summarised according to CTCAE grades and will be summarised as the maximum grade toxicity experienced within each cycle, and overall.

The proportion of patients achieving at least a PR (clonal response) within 3m, at 3m, within 6m and at 6m and the proportion of patients achieving an amyloidotic organ response within 3m and 6m will be presented in tabulated form. Corresponding 90% and 95% confidence intervals will also be presented. Responses at 3 and 6 months will be broken down by response achieved, and by organ (for organ response).

Time to amyloidotic organ response and time to maximum response will be calculated using the Kaplan Meier method. Median time to amyloidotic organ response and median time to maximum response will be presented, with corresponding 95% confidence intervals.

The proportion and number of patients alive at 6 months and patients progression free at 6 months will be presented with corresponding 90% and 95% confidence intervals. If appropriate, Kaplan Meier curves for progression free survival may be explored.

Each patient will be assessed for their maximum clonal response; the number and proportion of participants in each response category within 6 cycles of treatment will be presented with corresponding 95% confidence intervals. Patients who do not achieve a maximum response will be summarised as, "no maximum response".

Feasibility of delivering treatment according to protocol schedule will be summarised descriptively to include the number of patients requiring dose delays and/or reductions, the number of patients withdrawing from treatment, and reasons for dose delays / reductions and withdrawals. Time on treatment and reasons for stopping treatment will also be presented. The number of doses missed will be summarised overall and by cycle.

6. Reporting and Dissemination of the Results

Final analysis will be carried out after the last participant's last data item.

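### The primary grade 3 or 4 toxicity proportion stops at the last treatment cycle although adverse events are recorded for 30 more days, and it has no planned confidence interval

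*Protocol*

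**What the plan says.** **Window.** Protocol 18.1 names the endpoint as "Proportion of patients treated who experience any grade 3 or 4 CTCAE toxicity throughout all treatment cycles", and SAP 2.1 says the same. The derivation in Protocol 18.3 and SAP 2.3.1 puts the cycle in the singular and turns the proportion into a number: it "will be calculated as number of patients who experience any grade 3 or 4 CTCAE toxicity throughout their treatment cycle". The analysis sections (Protocol 19.3, SAP 5.3.2 Primary endpoints) state: "The number of patients experiencing any grade 3 or 4 CTCAE toxicity within all cycles of treatment will be summarised". The result is shown overall, by dose cohort and by cycle.

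**Collection.** Protocol 13.2.1 requires more than the endpoint uses: "All adverse events that occur between informed consent and 30 days post last trial treatment administration must be recorded". The assessment table in Protocol 11.0 also has adverse events recorded at the end-of-treatment and follow-up visits.

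**Precision.** Neither analysis section plans an interval for this proportion. For the response rates, the SAP adds: "Corresponding 90% and 95% confidence intervals will also be presented". Protocol 19.4 and SAP 5.3.2 (Secondary endpoints) plan the same two levels for the proportions alive and progression-free at 6 months.

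**Denominator.** SAP 5.1 gives a general rule: "percentages will be calculated using the total number of patients in the appropriate population as the denominator". Safety analyses are assigned to the safety set, which is defined in two ways. The synopsis (Protocol 1.1) takes every patient dosed with carfilzomib. Protocol 19.2 and SAP 3.2 also remove patients with a deviation judged relevant to safety.

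**The concern.** The expansion phase exists to characterise safety at the RD, and this proportion is its main safety result. Two features weaken it.

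First, the counting window is shorter than the collection window, and no section brings the final 30 days into the endpoint. A first severe event in that period is on the case report form but does not make the patient a case. The end of the last cycle is also not defined for someone who stops mid-cycle, so two analysts could place the cut-off differently.

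Second, the primary safety proportion would be shown without any statement of its uncertainty, next to secondary proportions that carry two intervals each. In a cohort of this size the uncertainty is large.

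**Working it through.** **The plan's own figures.** Escalation minimum 3 + 3 = 6 and maximum 3 levels × 6 = 18 match the breakdown in Protocol 19.1. The expansion size of 20 has no stated derivation, and no interval width is given for toxicity, so there is no precision figure to reproduce.

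**Inputs.**
- Treatment: "maximum of 6 x 28 day cycles" (Protocol 1.1), so at most 6 × 28 = 168 days.
- Collection: 30 days after the last trial treatment (Protocol 13.2.1).
- RD cohort: 20 expansion patients (Protocol 19.1) plus at least 6 from escalation (Protocol 8.1.3, Table 2), pooled under Protocol 19.2. This gives about 26.
- All event counts below are assumptions.

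**Step 1: time outside the endpoint window.** If thalidomide is taken to day 28 of the last cycle, the share of collection time from first dose that falls after the cycles is 30 / (28 × cycles + 30):

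| Cycles received | Calculation | Share |
|---|---|---|
| 6 | 30/198 | 15% |
| 3 | 30/114 | 26% |
| 1 | 30/58 | 52% |

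If the last administration is instead carfilzomib on day 15, collection runs 15 + 30 − 28 = 17 days past day 28. These are shares of time, not of events.

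**Step 2: effect on the proportion.** The endpoint is binary per patient, so only a patient with no earlier grade 3 or 4 event can change it. Each such patient adds 1/26 = 3.8 points. From an assumed 10/26 = 38.5%:
- 1 extra: 11/26 = 42.3%
- 2 extra: 12/26 = 46.2%
- 3 extra: 13/26 = 50.0%

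This range supposes that between 1/16 = 6% and 3/16 = 19% of the 16 patients without an earlier event have their first one in the final window.

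**Step 3: precision.** The exact (Clopper-Pearson) limits for x events in n patients are the α/2 quantile of Beta(x, n − x + 1) and the 1 − α/2 quantile of Beta(x + 1, n − x).

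| Assumed result | % | 95% CI | 90% CI |
|---|---|---|---|
| 6/26 | 23.1 | 9.0–43.6 | 10.6–40.5 |
| 10/26 | 38.5 | 20.2–59.4 | 22.6–56.4 |
| 13/26 | 50.0 | 29.9–70.1 | 32.7–67.3 |
| 20/26 | 76.9 | 56.4–91.0 | 59.5–89.4 |
| 10/20 (expansion only) | 50.0 | 27.2–72.8 | 30.2–69.8 |

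At n = 26 the 95% interval is up to about 40 points wide. With zero events, the upper limit is 1 − 0.025^(1/26) = 13.2%.

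**The case against.** Four stronger readings are tempting, and the documents do not support them.

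- **That late events disappear from the report.** They are recorded, SAEs are summarised separately, and SAP 5.3.2 (Secondary endpoints) adds: "Toxicity will be summarised according to CTCAE grades and will be summarised as the maximum grade toxicity experienced within each cycle, and overall". The overall maximum grade may include the final 30 days. The text does not say whether it does, so the exclusion is certain only for the primary proportion as worded.
- **That patients stopped for toxicity are the ones most often missed.** Treatment is held mainly for grade 3 or 4 non-haematological or grade 4 haematological events (Protocol 10.2), so these patients will often be counted already. Those at risk of being missed are patients with no earlier grade 3 or 4 event.
- **That the result will be a bare count.** The endpoint is named a proportion and SAP 5.1 supplies a general denominator, so a percentage can be expected. Calling it a number is loose drafting. What is missing is the interval and an unambiguous safety set.
- **That the rate is known to be understated.** The size is unknown and could be zero. In the carfilzomib study in AL amyloidosis described in Protocol 2.1.3.4, seven patients had a grade 3 or higher event, with 11 evaluable. If rates here are similar, many patients would be counted early and few would be left to miss. That study also reports severe cardiac events after cycles 3 and 7, so later severe toxicity is plausible, but the text does not say whether those patients were still on treatment.

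It can also be said that the analysis is descriptive, that no toxicity threshold depends on an interval, and that a reader could compute one from n/N. All true. But the secondary proportions are equally descriptive and do get intervals, so this does not explain the omission for the primary one.

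**Conclusion.** The point stands in a limited form. The endpoint as worded leaves out a first grade 3 or 4 event that occurs after the last cycle, although the event is collected. Any resulting error can only make the primary rate look lower. Its size cannot be derived from the documents. The increase from 38.5% to between 42.3% and 50.0% rests on an assumed base of 10/26 and an assumed 1 to 3 late first events.

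The missing interval is certain. With about 26 patients, an observed rate near one half is compatible with true rates from roughly 30% to 70%, and the plan does not commit to showing this. The figure of 26 assumes a full expansion cohort and exactly six escalation patients at the RD.

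This is a worthwhile, inexpensive correction to a primary safety endpoint. It does not show that safety data would be lost, nor that the design is unsound.

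**What to change.** 1. In Protocol 18.1, 18.3 and 19.3 and SAP 2.1, 2.3.1 and 5.3.2 (Primary endpoints), define the endpoint as any grade 3 or 4 CTCAE toxicity from the first dose to 30 days after the last trial treatment. This also settles the cut-off for patients who stop mid-cycle.
2. Reconcile the two safety-set definitions (Protocol 1.1 against Protocol 19.2 and SAP 3.2) and name the resulting set as the denominator.
3. For the RD cohort, report n/N, the percentage and exact (Clopper-Pearson) 90% and 95% intervals, matching the levels planned for the secondary proportions.
4. Keep the by-cycle tables as a breakdown.

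**Cost.** A primary endpoint definition changes, so this needs a short protocol amendment as well as SAP wording. No new data, visits or patients are needed, because the events are already on the case report form. The reported rate may be slightly higher.

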18.2 Secondary endpoints

- Clonal response rate within 3m, at 3m, within 6m and at 6m
- Amyloidotic organ response rate within 3m and 6m
- Time to amyloidotic organ response
- Number of deaths at 6 months
- Number of patients progression free at 6 months
- Maximum response
- Time to maximum response
- Number of patients withdrawing from treatment
- Number of patients experiencing dose delays, and compliance profile of KTD.
- Relative Dose intensity

Exploratory

Additional exploratory endpoints may be collected; any additional endpoints will be fully detailed in the statistical analysis plan.

18.3 Endpoint definitions

- DLT and MTD are defined in section 8.1.4 and 8.1.5
- The proportion of patients treated who experience any grade 3 or 4 CTCAE toxicity will be calculated as number of patients who experience any grade 3 or 4 CTCAE toxicity throughout their treatment cycle.
- Clonal response rate (based on paraprotein and FLCs) is defined as the proportion of patients who achieve at least a PR within 3 months, at 3 months, within 6 months and at 6 months after trial registration.
- Amyloidotic organ response rate is defined as the proportion of patients who achieve organ response within 3 months and within 6 months of trial registration.
- Time to Amyloidotic organ response is defined as the time from the dose allocation to first achieving organ response.
- The number of patients experiencing dose delays will be defined as the number of patients experiencing delays in treatment with any of the study treatments.
- KTD compliance: Patients will be regarded as compliant to treatment where treatment is received as per protocol until withdrawal from treatment and have no more than 1 dose omission of Carfilzomib, 5 of Thalidomide or 1 of Dexamethasone during each cycle.
- Relative Dose intensity will be calculated as the percentage ratio between the received and planned dose intensities, where dose intensity is the cumulative dose divided by the duration of treatment.

